P&G states that their purpose is to improve the lives of the world's consumers, and are interested in knowing whether their products and services are effective in this capacity. Because it is a publicly-traded private, for-profit corporation, P&G must develop products that consumers find useful enough to purchase regularly. This study will help the company understand more fully how its products further their mission to improve lives, may help the company develop new marketing strategies for their products, or modify existing formulations of their products to be more effective at preventing intestinal colonization with potentially harmful microorganisms.

Introduction

Current State of Knowledge

Travelers' diarrhea (TD) is the most common travel-related illness reported by international travelers, affecting between 30–70% of all travelers (1). The incidence of TD varies by travel destination, duration of travel, season, travel activities, and personal traveler attributes. Some areas of the world are considered high-risk, including Asia and Africa, but also the Middle East, Mexico, and Central and South America (1). Previous placebo-controlled clinical trials with the prophylactic use of bismuth subsalicylate (BSS) demonstrated a significant reduction in the incidence of TD among those receiving the drug. A recent unpublished meta-analysis on the subject of BSS prophylaxis found that persons who took BSS while traveling internationally before the onset of gastrointestinal symptoms had a 3.5 times greater odds of remaining free of TD in comparison to those who received placebo (2). BSS is available in both liquid and tablet formulations; both formulations reduced TD at doses of either 60mL four times daily (4.2g/d) for the liquid formulation (3) or 2 tablets, four times daily (2.1 g/day) for a maximum of 3 weeks (3, 4, 5). BSS at 2.1 g/day protected 41–65% of participants (3, 5), while the liquid formulation protected 62% of participants (3). Studies suggest the lowest minimum dose for protection may be 1g daily taken in 2 doses, which provided 35% protection in one analysis (5) and 40% protection in others (3, 4). BSS had minimal side effects, but these may include nausea,

constipation, tinnitus, and blackening of the tongue and stool (5, 6). BSS may cause encephalopathy if taken in high doses for prolonged periods, but this is exceedingly rare and above the recommended dose (7, 8).

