9. Have had diarrhea (see Definitions) anytime in the previous 30 days, have diarrhea at the pre-travel consultation, or develop diarrhea before departure
10. Have been given doxycycline for malaria prophylaxis for the current trip (due to possible drug-drug interactions and decreased absorption of the doxycycline) (27)
11. Have an allergy to any component of the placebo tablets

Estimated Number of Participants

We anticipate enrolling approximately 500 participants (see Sample Size and Power Calculation).

Sample Size and Power Calculation

A sample size of 488 participants with full compliance to medications and questionnaires (244 participants in each arm) is needed to fulfill the objectives [anticipated incidence of the endpoint as 40% incidence of TD with a 30% minimum intervention protection ($0.40-[0.4 \times 0.30] = 0.28$) with an alpha of 0.05, and 80% power].

Recruitment and Enrollment

All international travelers undergo a screening questionnaire at their pre-travel consultation to determine eligibility. This short questionnaire includes questions regarding the travelers' [see **APPENDIX A**]:

1. Age
2. Travel destination(s)
3. Trip duration
4. Acute and chronic medical conditions, including diarrhea
5. Contraindications to BSS administration
6. All current medications, including antibiotic use within the 30 days before screening
7. Willingness to participate in the trial and comply with the data collection requirements

This screening questionnaire will be administered to the traveler by study personnel at The New York Center for Travel and Tropical Medicine. The purpose will be to exclude those travelers who do not meet all inclusion criteria and those who meet any exclusion criteria (see Participant Inclusion / Exclusion Criteria). Travelers who meet the inclusion criteria and do not meet any exclusion criteria will be introduced to the project objectives and procedures, including the procedures for biologic (stool) specimen collection (see Laboratory instruments).

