Participants will be provided two OMNIgene gut kits at their pre-travel consultation/enrollment visit once enrolled (see Biologic [Stool] Specimen Data Collection and Testing). These kits will come with instructions on use, handling, and shipment.

In the event that participants are able to provide a stool sample while in clinic for their pre-travel consultation/enrollment visit or during a non-study post-travel follow-up sick visit within 10 days of return, these samples will be aliquoted by study personnel at The New York Center for Travel and Tropical Medicine in the following manner:

*First, the required quantity will be placed in the participant's OMNIgene gut kit (per manufacturer directions) to be sent to CDC's Clinical and Environmental Microbiology Branch for resistome testing. The remainder will be frozen, and sent to CDC for analysis at a later date (note: OMNIgene gut kit does not allow for culture - a see Biologic [Stool] Specimen Collection and Testing). Only those participants who happen to have a biologic (stool) specimen collection completed at the clinic will have their stool analyzed by culture; this is not a requirement for participation and no additional compensation above that previously described will be offered.

Table 3. Schedule of LABORATORY events (secondary objective)

(Events from Table 2 still apply to these participants)

	Stages		
	Pre-travel	During travel	Post-travel
Biologic (stool) sample	X		X
Laboratory testing of stool	X		X

Analytic tests

Questionnaires: Data from the questionnaires will be analyzed for statistical significance comparing intervention vs placebo groups.

Biologic (stool) specimens: A highly multiplexed PCR assay detecting over 500 different AMR genes will be used to test the DNA extracted from all biologic (stool) specimens that were placed in the OMNIgene gut kit (see Biologic (Stool) Specimen Collection and Testing). Results will be analyzed to determine if the participants acquire gut AMR genes (changes to the “resistome”) as a result of travel and whether or not that change varied with the bismuth subsalicylate treatment received. Additionally, stool bacteriologic culture will be performed on those specimens submitted in clinic.

Intervention

We propose the inclusion of two arms to test BSS against placebo:

1. BSS 4 tablets po bid (2.1 grams total)
2. Placebo 4 tablets po bid

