Dosing will begin on the flight prior to arrival in the destination and will cease once they return home. The study medications must be taken twice daily (a morning and an evening dose); with time zone changes, the first dose should be taken to ensure that no longer than 12 hours passes before a subsequent dose.

Before departure, participants will be provided, free of charge, all needed study medication for the duration of their trip. Participants will be encouraged to take all doses of their medication and appropriately document on their daily during travel questionnaires if a dose was missed or taken off schedule.

Outcomes

The outcomes of this study will include:

	Favorable Outcome	Non-favorable Outcome
Hypothesis 1: Prevention of TD	Prevention of TD in the intervention group	TD in the intervention group at a rate similar to placebo; intervention drug side effects; adverse events

Hypothesis 2: Acquisition of AMR genes	Reduced or no presence of travel-associated gut AMR genes in the intervention group	No reduction in the presence of travel-associated gut AMR genes in the intervention group
---	---	---

The participant's study period will end in the following circumstances:

1. The traveler meets criteria for removal (see Criteria for Removal from the Study)
2. The participant voluntarily withdraws from the study (see Procedures for Implementing and Documenting Informed Consent)
3. The participant completes all study activities and submits all study questionnaires and biologic (stool) specimens
4. The participant is lost to follow-up

The participants will be instructed at enrollment to stop the study medication for any of the following reasons (although they will still be instructed to answer their questionnaires and submit biologic [stool] specimens as scheduled):

1. Antibiotics or BSS (either provided by the study personnel for TD treatment, or taken as an over-the-counter remedy) are taken for TD or for another medical condition
2. Any severe adverse events as described, such as signs and symptoms of salicylism or neurotoxicity, occur
3. Hospitalization for any reason

Barring the reasons listed above, the study medication should be taken throughout the trip duration, even if diarrhea occurs, if possible.

Criteria for Removal from the Study

Participants will be removed from the study when any of the following criteria apply:

1. Do not complete the pre-travel questionnaire (see Definitions for compliance)
2. Loss to follow-up (see Definitions)

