APPENDIX C: Pre-travel Questionnaire

Pre-travel Questionnaire

PARTICIPANT UNIQUE ID: _____

GROUP ID: _____

[Please review the screening questionnaire with the participant.]

Have there been any changes to the screening questionnaire making the participant ineligible to participate?

- a. Yes
- b. No

If yes, please describe:

Demographics

Age (in years): _____

Sex (M/F): _____

Race:

- a. White or Caucasian
- b. Black or African American
- c. American Indian or Alaskan native
- d. Asian or Pacific Islander
- e. Other (please specify) _____
- f. Don't know
- g. I would rather not answer

Ethnicity:

- a. Hispanic
- b. Non-Hispanic

Medical History

2. Do you have any medical conditions or illnesses?

- a. Yes
- b. No
- c. Don't know
- d. I would rather not answer

If yes to question 1, please list them all.

3. Do you have recurrent or persistent tinnitus (ringing in the ears)?

- a. Yes
- b. No
- c. Don't know
- d. I would rather not answer

4. Do you take any medications on a regular basis?

- a. Yes
- b. No
- c. Don't know
- d. I would rather not answer

If Yes to question 3, please list them all:

1.	4.
2.	5.
3.	6.

5. Have you taken any oral or intravenous (IV) antibiotics in the past 90 days for any reason (e.g., azithromycin [Zithro-max], ciprofloxacin [Cipro], rifaximin [Xifaxan], doxycycline or minocycline, metronidazole [Flagyl], cotrimoxazole [Bactrim or Septra], penicillins [e.g., amoxicillin or Augmentin], or cephalosporins [e.g., Keflex])?

- a. Yes
- b. No
- c. Don't know
- d. I would rather not answer

If yes to question 4, please give the antibiotic name, start date, duration, and illness taken for:

No.	Antibiotic Name	Start Date (MM/DD/YYYY)	Duration (Days)	Illness taken for
1				
2				
3				
4				
5				
6				

6. In the past 30 days, have you taken a probiotic? -

Probiotics are live microorganisms (such as certain types of bacteria) that may benefit the health of the person consuming them. Yogurts and other fermented dairy products are probiotics. Probiotics can also take the form of capsules, pills, or powders. Probiotics also include any foods or drinks labeled as containing "live and active cultures" or "probiotics."

- a. Yes

- b. No
- c. Don't know
- d. I would rather not answer

Travel History

7. Have you traveled internationally in the past 90 days?

- a. Yes
- b. No
- c. Don't know
- d. I would rather not answer

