APPENDIX I: Data Analysis Table Shells

Table 1. Baseline Characteristics of Participants

	BSS	Placebo	P-value
Demographics			
Age			
Sex			
Race			
Ethnicity			
Medical History			
Chronic medical conditions			
Tinnitus			
Antibiotics between 30 to 90 days prior to travel			
Probiotics within 30 days			
Travel			
Duration of travel			
Primary reason for travel			
Secondary reasons for travel			
Attended provider (by type)			

Table 2. Odds ratios (OR) of TD associated with BSS among international travelers, adjusting for select factors

	Total, N	TD, %	OR (95% CI)
Tablets			
BSS			
Placebo			Ref
Age groups, years			
≥18			
Sex			
Male			
Female			Ref
Race/ethnicity			
Travel region			
Travel duration			

Table 3. The proportion of participants having resistance genes before and after travel; acquiring, losing, or maintaining genes after travel

	All participants	BSS	Placebo	P-value
Pre-travel				
Gene 1				
Gene 2				
Gene 3				
Gene 4				
...				
Post-travel				
Gene 1				
Gene 2				
Gene 3				
Gene 4				
...				
Acquisition of gene				
Gene 1				
Gene 2				
Gene 3				
Gene 4				
...				
Loss of gene				
Gene 1				
Gene 2				
Gene 3				
Gene 4				
...				
Maintenance of gene				
Gene 1				
Gene 2				
Gene 3				
Gene 4				
...				

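### BSS side effects count in the Hypothesis 1 outcome, but no table shell reports them on treatment and the only routine analysis reaching them is a significance test between arms

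*Combined protocol and SAP*

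**What the plan says.** The Outcomes section lists, as the non-favorable result for Hypothesis 1, "TD in the intervention group at a rate similar to placebo; intervention drug side effects; adverse events". Harm is therefore part of how the primary hypothesis is judged.

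Current State of Knowledge names the expected effects: "BSS had minimal side effects, but these may include nausea", followed by constipation, tinnitus and blackening of the tongue and stool. Appendix D gives each of these a daily tick-box, and question 3 of the post-travel questionnaire asks about them again. Nausea, vomiting and abdominal pain sit on the same diary checklist as diarrhea, with no field for severity or cause. Before travel, Appendix C question 3 asks "Do you have recurrent or persistent tinnitus (ringing in the ears".

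On analysis, the Questionnaires paragraph of Analytic tests says "Data from the questionnaires will be analyzed for statistical significance comparing intervention vs placebo groups". It names no test, population, event definition or estimate. Appendix I has three shells: baseline characteristics, in which tinnitus is a medical-history row; "Table 2. Odds ratios (OR) of TD associated with BSS among international travelers, adjusting for select factors"; and resistance genes. None has a row for a harm during treatment. A comparison of serious outcomes by a data safety monitoring board is mentioned under Response to New or Unexpected Findings, but only if the IRB asks for it, and the plan does not expect to need it.

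**The concern.** The findings are meant to inform advice to travelers about a preventive drug, so tolerability matters alongside efficacy. Two difficulties follow from leaving the harm analysis to a general statement about significance.

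First, the trial is sized for TD. For an uncommon harm, a P-value above 0.05 is the likely result even if the drug doubles the rate, and such a result is easily read as reassurance. Nothing in the plan calls for an estimate and interval that would show which excess is still compatible with the data.

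Second, some symptoms are both named drug effects and features of TD. If BSS prevents TD, it removes TD-related nausea while possibly adding its own. A comparison over all days gives the balance of the two. That is a legitimate quantity, but it does not by itself show the side effects that the Outcomes section names.

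**Working it through.** **The plan's own figure.** Sample Size and Power Calculation states "A sample size of 488 participants with full compliance to medications and questionnaires (244 participants in each arm) is needed", from "anticipated incidence of the endpoint as 40% incidence of TD with a 30% minimum intervention protection" "with an alpha of 0.05, and 80% power". With p1 = 0.40, p2 = 0.40 − 0.4 × 0.30 = 0.28 and mean 0.34, the two-sided pooled formula gives

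n = [1.96·√(2 × 0.34 × 0.66) + 0.842·√(0.40 × 0.60 + 0.28 × 0.72)]² / 0.12² = 243.4, hence 244 per arm and 488 in all.

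The stated size reproduces, with power 80.1%. It concerns TD only; the plan gives no figure for any harm. Planned enrollment is about 500, or 250 per arm.

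**Power for an uncommon harm** (2% and 4% are assumptions; the plan gives no rates).

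- Standard error under the null: √(2 × 0.03 × 0.97 / 250) = 0.01526.
- Standard error under the alternative: √((0.02 × 0.98 + 0.04 × 0.96) / 250) = 0.01523.
- Power = Φ[(0.02 − 1.96 × 0.01526) / 0.01523] = Φ(−0.65) = 0.26. At 244 per arm it is 0.25.
- 95% interval half-width: 1.96 × 0.01523 = 0.030. Observed rates of 2% and 4% (5 and 10 people of 250) would give a difference of 2.0 points, interval about −1.0 to 5.0. The interval shows that an excess of up to 5 points is not excluded; the P-value alone does not.
- At 244 per arm, 80% power needs a rise from 2% to about 7.4%, from 5% to 12.1%, or from 10% to 18.9%.

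**Net effect on nausea.** Let q be the share of TD cases with nausea, d the share of users in whom BSS causes nausea independently of TD, and b the background nausea. All three are assumptions.

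- Placebo: 1 − (1 − 0.40q)(1 − b).
- BSS: 1 − (1 − 0.28q)(1 − b)(1 − d).
- Setting these equal, b cancels, and drug-caused nausea is exactly offset at d = 0.12q / (1 − 0.28q).

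With b = 0:

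| q | Placebo | BSS, d = 5% | BSS, d = 10% | Fully offset at d = |
|---|---|---|---|---|
| 30% | 12.0% | 13.0% | 17.6% | 0.036/0.916 = 3.9% |
| 50% | 20.0% | 18.3% | 22.6% | 0.060/0.860 = 7.0% |
| 70% | 28.0% | 23.6% | 27.6% | 0.084/0.804 = 10.4% |

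The offset of 3.9% to 10.4% is about 10 to 26 people of 250. Adding 10% background nausea at q = 50% and d = 5% gives 28.0% against 26.5%, the same pattern.

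The rise in any-nausea that the drug causes among BSS users in this model is d(1 − 0.28q). At d = 5% this is 4.6, 4.3 and 4.0 points for q = 30%, 50% and 70%, because some drug-caused nausea falls in people who have TD nausea anyway.

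**Tinnitus.** It is not a TD symptom, so there is no offset. Appendix C is completed before departure and dosing starts on the flight, so question 3 describes people before their first dose. Those who already have tinnitus may tick the diary item in either arm, which adds noise.

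**The case against.** A reader might infer that harms will go unreported. The documents do not support that. The Analytic tests sentence covers all questionnaire data, the Outcomes table names side effects and adverse events, and Table 2 of the protocol schedules adverse-event reporting during and after travel. The presentation is unspecified; omission is not planned. Nor does the plan commit to bare, unadjusted P-values: it names no test, and the TD shell in Appendix I uses adjusted odds ratios with 95% intervals.

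A reader might also call the all-days nausea comparison biased. It is not. Under randomization it estimates the total effect of BSS on nausea without bias from TD, and a traveler may care most about exactly that. It answers a different question from how much nausea the drug causes.

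The size depends on rates that the documents do not give. At q = 30% and d = 5% the crude comparison still leans toward harm (13.0% against 12.0%), and at d = 10% it does so for q = 30% and 50%. The claim that a given harm would look like a benefit is therefore conditional, and it would be wrong to put the drug-caused excess at a fixed 5 points.

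Pre-existing tinnitus is balanced between arms in expectation and is shown in the baseline table, so it dilutes the comparison and does not favor either arm. Reporting new onset is a refinement.

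Finally, days before first TD depend on a post-randomization event that BSS is expected to change, and nausea on a day with fewer than three loose stools may be early TD. Such a split cannot carry a causal conclusion. All of these points stand. They narrow the concern but leave the missing harm estimate in place.

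**Conclusion.** The point holds as a gap in how harms will be estimated and shown. Harms belong to the Hypothesis 1 outcome and are collected daily, yet the only routine analysis reaching them is a significance test, and no shell presents them on treatment. With about 250 per arm, that test has about 26% power for an assumed 2% against 4%, so non-significance would not show safety. For nausea, vomiting and abdominal pain, the all-days result is a valid net effect that can understate drug-caused symptoms if BSS prevents TD. For nausea, full offset occurs at about 4% to 10% of users under the plan's TD rates and an assumed q of 30% to 70%, with drug-caused nausea independent of TD. The offset does not extend to tinnitus or to dark tongue or stool. The primary TD analysis is unaffected.

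**What to change.** Add one safety table to Appendix I, by arm as randomized, among participants who took at least one dose.

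- For each symptom named in Current State of Knowledge or in the adverse-event section that the questionnaires record, give number, percentage, risk difference and 95% confidence interval. This replaces the general significance test for these items. Slurred speech, muscle weakness, increased sweating and increased thirst have no box of their own in Appendix D and can appear only through the free-text item; a footnote should say so.
- Report tinnitus as new onset, leaving out those who answered yes to Appendix C question 3.
- For nausea, vomiting and abdominal pain, keep the all-days comparison as the main result. Beside it, show days before the first TD day, with diary days at risk as denominator, labelled descriptive because it conditions on an event that BSS may change and may include early TD symptoms.
- Name this table as the source for the harm part of the Hypothesis 1 outcome.

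The cost is one extra table from data already collected, and a descriptive split that needs cautious reading. No study procedure changes.
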